6.7 BASELINE, TIME WINDOWS AND CALCULATED VISITS

Baseline is defined as the last observation at, or prior to Visit 2. Hence, if a subject is randomized at Visit 2, but does not start trial medication until a future visit (e.g., Visit 4), then his/her baseline is the latest assessment performed at Visit 2. However, for laboratory safety measurements, the last value prior to the first drug administration will be considered as the baseline value.

Planned and actual test days are included in the analysis data sets and are calculated relative to the beginning of treatment as indicated in Table 6.7: 1 below.

For efficacy measurements, only one observation per time window will be selected for statistical analysis –the first one in the corresponding time window. If there are two observations which have the same difference in days to the planned day, or if there are two observations on the same day, the first value will be selected. If an observation is available on the last day of treatment, this observation will be preferably selected over any later observation that is still within the time window. Assignment of efficacy observations to visits based on time windows will be based on the non-imputed (observed) data. Repeated and unscheduled efficacy measurements will be assigned to the nominal visits according to the time windows described in Table 6.7: 1.

For safety measurements, data collected at all visits will be used. For repeated and unscheduled safety measurements for the same visit on treatment, the worst of these will be selected for analysis. In the case for which there is no standard reference direction for the safety parameter, the average of all values for the same visit will be used for analysis.

Visit	Relative to treatment start	
	Planned test day	Actual test day
2	1	Day 1 – Day 2

Table 6.7: 1Planned and actual study days

c42059532-01

Proprietary confidential information © 2023 Boehringer Ingelheim International GmbH or one or more of its affiliated companies.

3	8	Day 3 – Day 12
4	15	Day 13 – Day 19
5	22	Day 20 – Day 26
6	29	Day 27 – Day 33
7	36	Day 34 – Day 40
8	43	Day 41 – Day 47
9	50	Day 48 – Day 52
10/EOT	57 for completed subjects	Day 53 – treatment stop date (stopdt) + 7 days
eEOT	N/A (for early discontinued subjects)	Date of the last administration of trial medication + 7 days (for early discontinued subjects).

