7.4 PRIMARY OBJECTIVE ANALYSIS

7.4.1 Main analysis

The primary endpoint is the change from baseline to Week 8 in CAPS-5 total score. Baseline refers to the measurement recorded at randomization (Visit 2), if data at Visit 2 is missing, then data from Visit 1 will be considered baseline. The primary analysis of the primary endpoint will use a hybrid estimand that combines the treatment policy and hypothetical estimands as detailed in Section 6.3.

MMRM analysis

The change from baseline in CAPS-5 total score at Week 8 for each dose group as well as the corresponding variance-covariance matrix are estimated by a mixed effects model repeated measure (MMRM) including the fixed categorical covariates of treatment, and the stratification indicator of presence of significant childhood trauma (yes vs. no), the continuous fixed covariates of baseline CAPS-5 total severity score and time since index event (in years) and the treatment-by-visit interaction. Patient is considered as a random effect. Visit will be treated as a repeated measure with an unstructured covariance matrix used to model the within subject variability. The Kenward-Roger approximation will be used to estimate the denominator degrees of freedom. Analyses will be implemented using SAS 9.4 PROC MIXED. FAS is used for the primary analysis of the primary efficacy endpoint.

More specifically, the change in CAPS-5 total score from baseline (Visit 2), at Visits 2, 6, and 10 (Weeks 0, 4, and 8) will be evaluated using an MMRM accounting for the following sources of variation: 'treatment', 'visit', 'presence of significant childhood trauma (yes vs.no), time since index event (in years) and 'baseline CAPS-5 total score' as continuous covariates, and treatment-by-visit interaction, as well as the random 'subject' effect. The methods described in Section 10.1 will be utilized to resolve model non-convergence.

SAS code for MMRM:

The following SAS code will be used to calculate the MMRM.

PROC MIXED DATA=indata cl method=reml;

CLASS visit trt stratum subject;' MODEL ept = stratum visit*trt time_since_index base / ddfm=kr s CL; REPEATED visit / subject= subject type=un r rcorr; LSMEANS visit*trt / pdiff=all om cl alpha=**0.05** slice=visit;

RUN;

Results of the MMRM (N, mean, SE and 95% CI per dose group and timepoint) will be presented in tables and displayed graphically.

c42059532-01

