7.5.2 Secondary objective analysis

Logistic regression analysis

[figure not shown]
The binary secondary endpoints of CAPS-5 response (defined as \geq 30% CAPS-5 reduction from baseline at Week 8 and defined as \geq 50% CAPS-5 reduction from baseline at Week 8) will each be analyzed through a logistic regression model to obtain an estimate of the population odds ratio (OR) and associated confidence intervals between active arms and placebo. This logistic regression will be adjusted for fixed factors of treatment and presence of significant childhood trauma (yes vs. no). The analysis will be performed on the FAS. Adjusted odds ratios together with 95% confidence intervals will be used to quantify the effect of treatment, comparing treatment to placebo.

The SAS code for the logistic regression model is as follows:

```
proc logistic data=indata;
class trt stratum/ param=GLM; /* include (ref="placebo") for trt*/
model resp = trt base stratum / link=LOGIT covb;
lsmeans trt / cl;
run;
```

Adjusted odds ratio together with 95% confidence intervals, comparing all treatments to placebo, will be presented.

The secondary endpoint of change from baseline in PTSD Checklist for DSM-5 (PCL-5) total severity score at Week 8 will be analyzed using an MMRM model like that described for the primary analysis of the primary endpoint to obtain the adjusted change from baseline at Week 8 for BI active arm versus placebo.

Proprietary confidential information © 2023 Boehringer Ingelheim International GmbH or one or more of its affiliated companies.

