The very first part of Table 7.9.3:1, 'Demographics, Disposition and Baseline conditions' will be analyzed as stated in Sections 7.1-7.4. The subsequent analyses that pertain to 'Primary and secondary endpoints' will be analyzed via the methods discussed in Sections 7.4.1 and 7.5.2. Standard safety will be evaluated according to the methods described in Section 7.8. And lastly, Table 7.9.3:1 ends with a set of 'Exploratory' analyses that will be analyzed descriptively, hence the change from baseline at Week 8, as well as the percent change from baseline (across treatment arms and for the total) will be provided.

Proprietary confidential information © 2023 Boehringer Ingelheim International GmbH or one or more of its affiliated companies.

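### SAP 7.4.1 makes Week 0 a response visit in the primary change-from-baseline MMRM: that response is zero by construction, so the REML fit has no optimum and the covariate adjustment collapses

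*SAP*

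**What the plan says.** SAP 7.4.1 takes baseline as the Visit 2 CAPS-5 score and adds that "if data at Visit 2 is missing, then data from Visit 1 will be considered baseline". SAP 6.7 agrees: "Baseline is defined as the last observation at, or prior to Visit 2". Section 7.4.1 then specifies the model in more detail: "the change in CAPS-5 total score from baseline (Visit 2), at Visits 2, 6, and 10 (Weeks 0, 4, and 8) will be evaluated". The code uses "PROC MIXED DATA=indata cl method=reml", "MODEL ept = stratum visit*trt time_since_index base / ddfm=kr s CL" and "REPEATED visit / subject= subject type=un r rcorr". The input data set `indata` is not defined, and nothing in the available text removes Visit 2 from it. Non-convergence is referred to SAP Section 10.1, which is not in the available text.

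Two other analyses depend on this section. For the interim, SAP 7.9.3 says: "The subsequent analyses that pertain to 'Primary and secondary endpoints' will be analyzed via the methods discussed in Sections", and the sections it names are 7.4.1 and 7.5.2. For PCL-5, SAP 7.5.2 says the endpoint "will be analyzed using an MMRM model like that described for the primary analysis of the primary endpoint" and lists no visits. Protocol 7.2.3 names no Week 0 response, so the problem arises in the SAP.

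**The concern.** At Visit 2 the change from baseline is the score minus itself. It is 0 for everyone with a Visit 2 score. If Visit 1 stands in as baseline, the Week 0 change is missing. A repeated-measures model with its own variance for each visit cannot be fitted to a response that never varies. The covariates enter as main effects only, so the coefficients that should adjust Week 8 must also fit the Week 0 zeros, and the value that fits them is 0.

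At stake is the adjustment for baseline severity, childhood trauma and time since index event in the primary analysis, together with a well-defined standard error. The same model supplies the interim Week 8 effect, from which the standardized effect size in protocol 7.2.8 is judged for a possible early stop.

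**Working it through.** **Inputs from the documents.** Response visits, baseline definition and code are from SAP 7.4.1. The sizes are from protocol 7.5: 100 evaluable per arm at the final analysis and 60 at the interim. These agree with the planned numbers randomized: 200/0.7 = 285.7, rounded up to 286, and 120/0.7 = 171.4, rounded up to 172. The plan gives no CAPS-5 SD and no figure for the precision of the MMRM.

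**Step 1. The likelihood has no optimum (no assumed inputs).** Let s0 be the Week 0 SD and N the number of patients with a Week 0 row.
- The Week 0 mean has five coefficients: two arm means plus stratum, time since index event and baseline. Setting all five to 0 makes every Week 0 residual exactly 0.
- As s0 falls, the log-determinant of the covariance contributes N ln(s0²). The REML term for the fixed effects gives back 5 ln(s0²).
- The net term in -2REML is (N - 5) ln(s0²), which goes to minus infinity.
- Each tenfold drop in s0 lowers -2REML by (N - 5) × 2 ln 10 = (N - 5) × 4.605. At N = 200 this is 195 × 4.605 = 898. At N = 120 it is 115 × 4.605 = 530.

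**Step 2. Numerical confirmation.** One simulated trial was fitted with 100 per arm. Assumed: change SD 10, baseline SD 8, baseline-change correlation -0.4. s0 was held fixed and all other covariance parameters were optimized.

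| s0 | -2REML | Shared baseline slope |
|---|---|---|
| 1 | 3231.7 | -0.01514 |
| 0.1 | 2333.7 | 0.00151 |
| 0.01 | 1435.7 | 0.00015 |
| 0.001 | 537.6 | 0.00002 |

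Each step is 898, as the formula gives. The Week 8 difference goes to -1.279, the unadjusted value. With Weeks 4 and 8 only, the model has a finite optimum (-2REML 2834.6), a baseline slope of -0.519 and a Week 8 difference of -1.149. The same divergence and vanishing slope appear with 30% of Week 8 values missing.

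**Step 3. Precision (rests on assumptions).** Assumed: change SD 10 at Week 4 and 12 at Week 8, correlation 0.7 between them, and a Week 8 effect of 0.35 × 12 = 4.2 points. There were 1000 complete-data trials per setting, fitted by REML-EM in Python, not SAS, with no Kenward-Roger step and no floor on s0.

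| Baseline-change correlation | Per arm | Median Week 8 SE, Week 0 included | Median Week 8 SE, Weeks 4 and 8 only |
|---|---|---|---|
| -0.2 | 100 | 1.694 | 1.669 |
| -0.4 | 100 | 1.690 | 1.564 |
| -0.6 | 100 | 1.690 | 1.365 |
| -0.2 | 60 | 2.180 | 2.154 |
| -0.4 | 60 | 2.191 | 2.027 |
| -0.6 | 60 | 2.179 | 1.765 |

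- Hand check at -0.4 with 100 per arm: unadjusted 12 × √(2/100) = 1.70; adjusted 1.70 × √(1 - 0.16) = 1.56.
- Equivalent loss of patients at -0.4: 1 - (1.564/1.690)² = 0.14, about 29 of 200. At -0.2 it is 0.03 (6 patients) and at -0.6 it is 0.35 (70 patients).
- With 100 per arm, the Week 8 estimate moves by a median of 0.36 points (0.20 to 0.58 over the range).
- With Week 0 included, all three covariate coefficients were below 3e-11 in absolute value in every trial. The Week 8 estimate was within 0.012 of the raw mean difference. Mean estimates were unbiased in both fits.
- Missing-data check: 143 per arm, 30% missing at Week 8 depending on the Week 4 change, 200 trials. At -0.4 the SE was 1.55 with Week 0 and 1.46 without.

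**Step 4. The reported SE is not determined.** In Step 3, Fisher scoring agreed with EM, but a ridged Newton-Raphson stalled and gave 1.56 to 1.71. In the Step 2 data set, the Week 8 SE was 4.63 along the path of best likelihood and 1.444 with Week 0 held uncorrelated, against 1.340 for the correct model.

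**The case against.** The strongest reply is that this is loose wording. Visits 2, 6 and 10 are the scheduled CAPS-5 visits, and a programmer would probably drop Visit 2. If not, the fit would probably fail and Section 10.1 would apply. SAS was not run, so the practical outcome is unknown. That last point stands, and it is why the SE of 1.69 is an illustration and not a forecast. The rest does not rescue the text. The sentence directly above the code says the opposite of what the programmer would have to do. A non-convergence fallback also leaves the zero rows in the data. If the fallback were compound symmetry, for example, the zeros would deflate the common variance: in 100 simulated trials under the Step 3 assumptions the median Week 8 SE was 1.20, against an empirical SD of 1.57.

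Second, protocol 7.2.3 can be read as baseline-by-visit. On that reading the Week 8 baseline slope survives (-0.515 in the Step 2 data set) and most of the precision loss goes away. The likelihood is still unbounded, stratum and time since index event still share one slope, and the SAP code contains no such interaction.

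Third, a repeated Visit 2 rating could give a non-zero Week 0 change, because SAP 6.7 takes the first value in a window for efficacy but the last for baseline. This would be rare and would not make Week 0 a meaningful response.

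Fourth, protocol 7.1 plans no formal test and 7.2.3 calls the p-values and intervals descriptive. That is correct and limits the consequence.

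**Conclusion.** The concern holds: SAP 7.4.1 is wrong as written and should be fixed. Two results need no assumed inputs: the REML criterion has no optimum, and the shared covariate coefficients are driven to 0. The loss of precision does depend on assumptions. It is about 14% of patients at a baseline-change correlation of -0.4, and 3% to 35% over -0.2 to -0.6, with SDs that are not in the documents. The estimate stays unbiased under randomization with complete data. What PROC MIXED or Section 10.1 would produce is not established. The sample-size figures in protocol 7.5 are not affected.

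**What to change.** In SAP 7.4.1, state that the response visits are Visits 6 and 10 (Weeks 4 and 8) and that Visit 2 enters only as the baseline covariate. Restrict the data or code to match, for example `WHERE visit in (6,10)`, which is the SAP's own list without Visit 2. Apply this to the interim run, and state the response visits for the PCL-5 model in 7.5.2.

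Two clarifications belong in the same edit. Say whether baseline enters as a main effect or by visit, so that SAP and protocol agree. Also say what happens to early end-of-treatment CAPS-5 scores that Table 6.7:1 maps to other visits: the SAP's visit list already leaves them out, but its code has no filter.

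The core change costs one sentence and one line of code or data set specification. It needs no new data and places no burden on patients.

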7.5 SECONDARY OBJECTIVE ANALYSIS

7.5.1 Key secondary objective analysis

This section is not applicable as no key secondary endpoint has been specified in the protocol.

7.5.2 Secondary objective analysis

Logistic regression analysis

[figure not shown]
The binary secondary endpoints of CAPS-5 response (defined as \geq 30% CAPS-5 reduction from baseline at Week 8 and defined as \geq 50% CAPS-5 reduction from baseline at Week 8) will each be analyzed through a logistic regression model to obtain an estimate of the population odds ratio (OR) and associated confidence intervals between active arms and placebo. This logistic regression will be adjusted for fixed factors of treatment and presence of significant childhood trauma (yes vs. no). The analysis will be performed on the FAS. Adjusted odds ratios together with 95% confidence intervals will be used to quantify the effect of treatment, comparing treatment to placebo.

The SAS code for the logistic regression model is as follows:

```
proc logistic data=indata;
class trt stratum/ param=GLM; /* include (ref="placebo") for trt*/
model resp = trt base stratum / link=LOGIT covb;
lsmeans trt / cl;
run;
```

Adjusted odds ratio together with 95% confidence intervals, comparing all treatments to placebo, will be presented.

The secondary endpoint of change from baseline in PTSD Checklist for DSM-5 (PCL-5) total severity score at Week 8 will be analyzed using an MMRM model like that described for the primary analysis of the primary endpoint to obtain the adjusted change from baseline at Week 8 for BI active arm versus placebo.

Proprietary confidential information © 2023 Boehringer Ingelheim International GmbH or one or more of its affiliated companies.

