7.2.4 Secondary objective analyses

For the continuous efficacy endpoint of change from baseline on the PTSD Checklist for DSM-5 (PCL-5) total score at Week 8, the same strategy for handling the intercurrent events in the primary estimand analysis and a similar MMRM analysis used for the primary efficacy endpoint will be conducted to obtain the adjusted mean treatment effect between BI and placebo in terms of change from baseline to Week 8. This MMRM model includes the discrete fixed effects of treatment at each visit, fixed categorical covariate of the stratification factor of presence of significant childhood trauma (yes vs. no), and continuous fixed effects

Page 97 of 148

Proprietary confidential information © 2023 Boehringer Ingelheim International GmbH or one or more of its affiliated companies

of time since index event (in years) and the corresponding baseline endpoint value at each visit. Visit will be treated as the repeated measure with an unstructured covariance structure to model the within-subject measurements. Subjects will be considered as a random effect. The primary treatment comparison is the contrast between treatment and placebo at Week 8.

A logistic regression adjusted for treatment and stratification factor of presence of significant childhood trauma (yes vs. no) will be used for binary endpoints.

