3. INTRODUCTION

The purpose of this TSAP is to provide analysis specifications that is to be reported in the final CTR. Also included in this TSAP are analysis specifications for an interim analysis, the results of which are to be reported in a synoptic report that is separate from the final CTR.

As per International Conference on Harmonisation (ICH) E9 (1), the purpose of this document is to provide a more technical and detailed elaboration of the principal features of the analysis described in the CTP, and to include detailed procedures for executing the statistical analysis of the primary and secondary variables and other data.

This Trial Statistical Analysis Plan (TSAP) assumes familiarity with the Clinical Trial Protocol (CTP), including Protocol Amendments. In particular, the TSAP is based on the planned analysis specification as written in CTP Section 7 "Statistical Methods and Determination of Sample Size". Therefore, TSAP readers may consult the CTP for more background information on the study, e.g., on study objectives, study design and population, treatments, definition of measurements and variables, planning of sample size, randomization.

R Version 3.3.2 with "DoseFinding" package (2) will be used for analyses based on Multiple Comparison Procedures and Modelling (MCPMod) and SAS® Version 9.4 will be used for all other analyses.

The main analyses of this TSAP will be conducted under the estimand concept. To quote ICH E9 R1, "An estimand is a precise description of the treatment effect reflecting the clinical question posed by a given clinical trial objective. It summarizes at a population level what the outcomes would be in the same patients under different treatment conditions being compared." So, an estimand is a way for the clinical trial protocol to address how intercurrent events will be handled. And according to ICH E9 R1, intercurrent events are events occurring after treatment initiation that affect either the interpretation or the existence of the measurements associated with the clinical question of interest. Or in other words, intercurrent events are occurrences after randomization that involve a change in treatment regimen.

c42059532-01

Proprietary confidential information © 2023 Boehringer Ingelheim International GmbH or one or more of its affiliated companies.

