5.2.2 Secondary endpoint(s)

CAPS-5

- Response defined as ≥30% CAPS-5 reduction from baseline at Week 8

[figure not shown]
- Response defined as ≥50% CAPS-5 reduction from baseline at Week 8

PCL-5

- Change from baseline on the PTSD Checklist for DSM-5 total score at Week 8

c42059532-01

Proprietary confidential information © 2023 Boehringer Ingelheim International GmbH or one or more of its affiliated companies.

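### SAP 7.5.2 describes one responder model in its text and fits another in its code, and the code does not say which outcome level is the event

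*SAP*

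**What the plan says.** Two of the three secondary endpoints are binary: CAPS-5 response at Week 8 at a 30% threshold ("Response defined as ≥30% CAPS-5 reduction from baseline at Week 8", SAP 5.2.2) and at a 50% threshold.

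The wording of the model agrees across the two documents. Protocol 7.2.4: "A logistic regression adjusted for treatment and stratification factor of presence of significant childhood trauma (yes vs. no) will be used for binary endpoints". SAP 7.5.2: "This logistic regression will be adjusted for fixed factors of treatment and presence of significant childhood trauma (yes vs. no". Neither mentions a baseline score. The quantity to report is also stated in SAP 7.5.2: "Adjusted odds ratios together with 95% confidence intervals will be used to quantify the effect of treatment, comparing treatment to placebo".

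The code printed in the same SAP section differs. It opens with "proc logistic data=indata", followed by "class trt stratum/ param=GLM; /* include (ref='placebo') for trt", and the model line is "model resp = trt base stratum / link=LOGIT covb". The extra term is `base`. No event level is named on the PROC or the MODEL statement; the only note about levels concerns the treatment reference. SAP Section 3 assigns this analysis to SAS: "SAS® Version 9.4 will be used for all other analyses".

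**The concern.** A pre-specified analysis should lead to one number. Here a programmer who follows the text and one who follows the code fit different models, and both can claim to have followed the plan. In logistic regression the choice affects more than precision. The odds ratio is non-collapsible, so conditioning on a prognostic baseline score changes the quantity being estimated, even in a perfectly randomised trial. If the choice is left open until the data are unblinded, it becomes a post hoc choice.

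The missing event level is a separate gap. For a binary outcome, PROC LOGISTIC without an event option, DESCENDING or a changed ORDER= models the first level in ascending order. This is SAS behaviour and not something the documents state. Whether the printed odds ratio refers to responding or to not responding then depends on how `resp` is coded, which the visible text does not say.

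Both responder endpoints are in the interim package (SAP 7.9.3, Table 7.9.3:1), and the sponsor's decision to stop or continue takes secondary objectives into account (protocol 7.2.8).

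**Working it through.** The plan attaches no figure to this analysis, so there is nothing to reproduce. The check compares text with code and then sizes each gap under stated assumptions.

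**1. Terms in the model**

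| Source | Treatment | Childhood trauma | Baseline score |
|---|---|---|---|
| Protocol 7.2.4, text | yes | yes | no |
| SAP 7.5.2, text | yes | yes | no |
| SAP 7.5.2, code | yes (`trt`) | yes (`stratum`) | yes (`base`) |

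The meaning of `base` is inferred. The primary MMRM code in SAP 7.4.1 uses the same name, and there the text lists baseline CAPS-5 as a covariate.

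**2. Size of the covariate gap**

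The documents give no prognostic strength for baseline CAPS-5 on response, so a range is assumed:
- log-odds of response = −0.4 + 0.5 × treatment − 0.2 × stratum + b × (centred baseline)
- baseline SD 8 points
- b between 0 and −0.10 per point

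The odds ratio conditional on baseline is exp(0.5) = 1.649 throughout. Averaging the response probability over baseline within each arm and stratum, and then forming the odds ratio, gives the large-sample value without `base`:

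| b per point | SD of the baseline term (8 × size of b) | OR with `base` | OR without `base` |
|---|---|---|---|
| 0 | 0 | 1.65 | 1.65 |
| −0.03 | 0.24 | 1.65 | 1.64 |
| −0.06 | 0.48 | 1.65 | 1.61 |
| −0.10 | 0.80 | 1.65 | 1.55 |

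The direction never changes, and if baseline is not prognostic the two values coincide. In one simulated data set per slope, with 100 per arm, the two fits differed by a few hundredths and in either direction: 1.82 without and 1.86 with `base` at b = 0; 1.48 and 1.46 at −0.03; 2.00 and 1.96 at −0.06.

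**3. Level modelled by default**

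| Coding of `resp` | First level in ascending order | Modelled as the event |
|---|---|---|
| 0/1 (1 = responder) | 0 | non-response |
| No/Yes or N/Y | No or N | non-response |
| Non-responder/Responder | Non-responder | non-response |
| 1 = yes, 2 = no | 1 | response |

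**4. Effect of modelling non-response**

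OR for response = [p_A/(1 − p_A)] / [p_P/(1 − p_P)], where A is active and P is placebo. OR for non-response is its reciprocal.

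For 50% against 40%: (0.50/0.50)/(0.40/0.60) = 1.50, and 1/1.50 = 0.67.

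With 100 evaluable patients per arm (protocol 7.5), assumed response rates and unadjusted Wald intervals:

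| Placebo, active | OR for response (95% CI) | OR for non-response (95% CI) |
|---|---|---|
| 40%, 50% | 1.50 (0.86–2.63) | 0.67 (0.38–1.17) |
| 40%, 55% | 1.83 (1.05–3.21) | 0.55 (0.31–0.96) |
| 25%, 35% | 1.62 (0.88–2.98) | 0.62 (0.34–1.14) |
| 25%, 40% | 2.00 (1.09–3.66) | 0.50 (0.27–0.92) |

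Logistic fits to the outcome and to its complement gave odds ratios whose product was 1.000, with and without `base`. The reversal is therefore exact and leaves the p-value unchanged.

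**5. Does anything else in the code cancel it?**

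No. The comment on the CLASS line calls for placebo as the treatment reference. Even without that option, the SAP short names (Table 6.1:1) sort Placebo after BI 125 mg, and the last level is the default reference under GLM coding. The LSMEANS line requests no differences or odds ratios, so the reported odds ratio would come from the procedure's default odds-ratio table, which is the output affected.

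**The case against.** The strongest reply is that the printed code is a template. Its CLASS line carries an instruction to the programmer to add an option, so level options were visibly left for completion, and the governing text is clear that the endpoint is response and the comparison is with placebo. The coding of `resp` may also be given in text that is not visible: the SAP cites Sections 10.1 and 10.4, whose content cannot be seen here. This stands as far as the event level goes, and it makes that part a clarification and not a demonstrated error.

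A reader might infer that the responder odds ratios will be reported upside down, so that a benefit reads as harm at the interim. The documents do not support that. The coding is unknown and at least one plausible coding gives the right direction. Protocol 7.1 plans no formal hypothesis testing, and inversion does not alter the p-value. SAP Section 7 has categorical data tabulated with counts and percentages by group, and the interim package carries the CAPS-5 mean change beside both responder endpoints. A reversed odds ratio would conflict with these on sight.

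It can also be said that the effect of `base` is small. That is fair on size. It does not remove the contradiction, which needs no assumption about coding: the text and code of one SAP section list different covariates. Nor does the template argument help here, since `base` is a term the author put in and not an option left out.

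**Conclusion.** The point holds on two levels of certainty.

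The covariate mismatch is certain from the documents: the SAP text and protocol 7.2.4 name two terms, the SAP code fits three. Under the assumptions above (conditional odds ratio 1.65, baseline SD 8, slope 0 to −0.10 per point), the large-sample odds ratio without baseline lies between 1.65 and 1.55. The difference is modest and in the same direction, but the plan still leaves open which adjusted odds ratio is meant. It would be wrong to read this as two analyses that could reach opposite conclusions about direction.

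The event-level gap is conditional. If `resp` is coded 0/1 or No/Yes, running the code as printed gives the reciprocal (0.67 in place of 1.50 in the example). The visible text does not settle the coding, and the accompanying percentages would probably expose the reversal. It deserves correction because the correction is nearly free. No wrong result has been shown.

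**What to change.** Covariates: keep baseline CAPS-5, which is already collected and is already a covariate in the primary MMRM. Add it to the model description in SAP 7.5.2 and record it as a change from protocol 7.2.4. Editing the SAP text alone would only move the mismatch to one between SAP and protocol. Dropping `base` from the code would also reconcile the documents, but it gives up the consistency with the primary analysis.

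Event level: state that `resp` = 1 means response, and write `model resp(event='1') = trt base stratum / link=logit covb;`. Put the placebo reference that the comment already asks for into the CLASS statement.

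Cost: one or two lines of code, one sentence of SAP text and a documented departure from the protocol wording. Trial conduct, data collection and sample size are unaffected. It should be done before the interim analysis is run.
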